one of three trained CM staff will turnover during the project's first two phases, each center will be required to identify one or more replacement CM staff. Thus, if one of the initially trained CM staff withdraws from the study for any reason during the Preparation or Implementation phase, a replacement CM staff will be immediately trained.

- c. *Community-based OUD treatment center patients (Patients).* Each center will agree to deliver CM to all patients newly admitted over a 6-month period. In addition, each center will be asked to enroll approximately one eligible CM patient per week to complete research assessment measures. Eligible patients will be: a) adult patients, b) newly admitted to the opioid treatment center within the past 30 days, and c) prescribed any FDA-approved OUD medication. To optimize ecological validity, exclusion criteria will be minimal and will only include issues that could interfere with the ability to complete a brief intake interview including acute intoxication, acute psychosis, acute mania, or cognitive impairment (prohibiting comprehension of the consent process), as reported by opioid treatment center staff or observed by research staff. We focus on newly admitted patients as opposed to those established in treatment because the need is highest among these patients: drop-out rates and missed doses are higher during the first 6 months of treatment (i.e., the "induction phase") than any subsequent period.

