- 5. **CM Procedures.** CM is a behavioral treatment in which providers deliver motivational incentives to patients for attaining specific treatment benchmarks. CM protocols have demonstrated effectiveness across various *reinforcement schedules* (immediate vs. delayed), *delivery schedules* (biweekly vs. weekly), and *behavioral targets* (abstinence vs. compliance).^{1,2} We will train staff from participating organizations in how to deliver a flexible, evidence-based CM protocol, which **targets compliance with opioid treatment** and **provides immediate reinforcement using escalating prize draws**. This protocol is supported by a robust literature that has shown: a) immediate reinforcement is associated with larger effect sizes than delayed;³ b) more frequent reinforcement is linked to better patient outcomes than less frequent or intermittent reinforcement;² and c) prize draws are less expensive, yet as effective (more cost effective) as vouchers.⁵ In addition, we completed pilot data collection with 12 opioid treatment centers as part of a NIDA funded pilot study (P20 GM125507) and centers indicated that they preferred to incentivize treatment compliance over abstinence or attendance at sessions.

The minimum goal will be for participating organizations to provide reinforcement in the form of a prize draw to patients at least once per week. Staff in the organizations will be responsible for monitoring patient compliance (defined further below) as part of the CM protocol.

For this study, we will train staff from participating OUD centers in a flexible CM protocol adapted from an evidence-based CM protocol initially created by [name], an international expert in CM delivery. Leadership of all participating organizations will define opioid treatment compliance as follows: Compliance rate = number of completed clinical

contacts per week / number of expected clinical contacts per week. Clinical contacts can be broadly defined as including medication doses, counseling sessions, and urine screens. Organizations will be allowed to determine the minimal compliance benchmark, and the weighting of clinical contacts to fit their organizational needs and preferences. In both conditions, organizations will be required to develop a clear CM compliance benchmark for earning prizes and a clear equation for how compliance would be calculated.

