For instance, Treatment Center A might report that they expect opioid patients to present daily for doses of opioid medication (i.e., methadone) and do not expect patients to have any other clinical contacts. Treatment Center A might also determine that their CM compliance benchmark is 80%: in other words, Treatment Center A will only reward patients who attain 80% compliance. Compliance at Organization A would be outlined as follows: Compliance rate = number of clinical contacts completed / number of clinical contacts (7 medication doses) expected to be completed. A patient who received 6 of 7 doses would have a compliance rate of 86% ($6 / 7 = 86\%$). This patient would receive a prize draw because they surpassed the 80% benchmark. By contrast, a patient who received 5 of 7 doses would have a compliance rate of 71% ($5 / 7 = 71\%$). This patient would not receive a prize draw because they did not meet or surpass the 80% benchmark.

Another treatment center, Treatment Center B, might report that they expect opioid patients to present weekly for opioid medication doses (i.e., buprenorphine), monthly for a counseling session, and monthly for a urine screen. This center might set a CM compliance benchmark of 100%: in other words, patients must attend 100% of expected clinical contacts to earn a prize draw. The number of expected clinical contacts would vary on a weekly basis. In some weeks, Organization B would have only 1 expected clinical contact (a dose of buprenorphine). In these weeks, Compliance at Organization B would be as follows: Compliance rate = number of completed clinical contacts / number of expected clinical contacts (1 dose). Patients who presented for buprenorphine would have a monthly compliance rate of 100% ($1 / 1 = 100\%$) and would earn a prize draw. Patients who did not present for their buprenorphine would have a monthly compliance rate of 0% ($0 / 1 = 0\%$) and would not earn a prize draw.

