In other weeks, patients at Organization B might have 3 clinical contacts expected (e.g., 1 medication dose, 1 urine screen, 1 counseling session). In these weeks, a patient who presented for only buprenorphine would have the following compliance rate: 1 actual visit / 3 expected visits = 33%, and would not receive a prize draw. Likewise, a patient that presented for only buprenorphine and a counseling session but missed the urine screen would have the following rate: 2 actual visits / 3 expected visits = 66%, and would not receive a draw. Patients would have to attend all 3 clinical contacts to receive a prize draw.

[figure not shown]
The CM protocol that staff will be trained in will consist of the following actions: 1) Review patient compliance for the week with patient using the organization definition of number of expected clinical contacts; 2) Clearly inform the patient if their compliance for week exceeded the organizational CM benchmark; 3) Clearly state the number of prize draws (if any) earned in the current session; 4) Administer CM prize draws as appropriate; 5) State number of draws patient can earn at the next session (goal-setting); 6) Praise patient's efforts towards compliance (even if the compliance benchmark was not met); and 7) Communicate confidence that patient's efforts will yield success in the future.

The evidence-based CM protocol⁶⁻⁸ that staff will be trained in will provide patients with increasing opportunities for winning cost-neutral (i.e., praise), \$1, \$20, and \$100 prizes for each week during which the CM compliance benchmark was attained. Draws increase by one for each week that compliance was attained. Failure to attain the benchmark or failure to attend the prize draw session resets draws for the next week down to one, with draws again escalating for sustained compliance. Patients will receive prize draws for up to 12 weeks, which is the median duration of the induction phase at participating centers (range

from 4 to 26 weeks). This progression will yield a maximum of 78 draws ($1+2+3+\dots+12$). Fishbowls will contain 500 slips; 250 state “good job!” but are not associated with a prize, 209 state “small,” 40 state “large,” and one “jumbo.” Using these probabilities and magnitudes of \$1, \$20, and \$100 for the three respective prize sizes, each draw has an average cost of \$2. Thus, for a 12-week protocol, each patient could earn 78 draws \times \$2/draw = \$156 in prizes.

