- i. **Implementation climate.** A 6-item measure of CM staff and leadership shared perceptions regarding the extent to which the innovation being implemented (i.e., CM) is expected, supported, and rewarded within their center.²⁵ Each item is scored on a 5-point Likert scale. This well-validated, brief measure was developed by Jacobs and colleagues, and following published guidelines, we calculate a scale mean for each staff member.
- ii. **Leadership engagement.** A 4-item measure of CM staff and leadership shared perceptions regarding the extent to which leadership is committed to, involved in, engaged in, and accountable for the implementation of the innovation (i.e., CM). Each item is scored on a 5-point Likert scale. Developed and validated as part of [name] current NIDA-funded project, this measure has demonstrated excellent internal reliability ($\alpha = .94$) and has been shown to be a significant predictor of staff-level implementation fidelity ($\beta = .18, p < .05$).²⁶

d. *Covariates.* We measure potential baseline covariates at the patient, staff, and organization level. These measures are only administered at baseline. Specific measures used include:

- i. **Baseline organization form.** A form measuring baseline characteristics including years of operation, number of patients served, and medications prescribed.
- ii. **Implementation Readiness.** A well-validated 12-item pragmatic measure developed by Shea and colleagues²⁷ will assess readiness to implement CM.
- iii. **CM Attitudes.** A brief measure of attitudes towards CM, as well as providers' perception of its effectiveness and acceptability will be administered. This measure was developed by the NIDA Clinical Trials Network and has been used in multiple NIDA funded studies.
- iv. **Provider demographics.** At the provider-level, we measure staff tenure, education level, and attitudes towards CM.

- v. Patient demographics. At the patient-level, we measure biological sex, race/ethnicity, age, and problem severity.
- vi. Patient clinical characteristics. At baseline, we administer a general measure of global health functioning. This scale was developed by the NIH funded patient-reported outcomes study and is used in multiple NIH funded studies.
- e. *Other Measures*. As noted in prior sections, we also collect some additional measures.

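### Medication is named as a covariate only at center level; each patient's medication at admission should be a pre-specified patient-level covariate

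*Combined protocol and SAP*

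**What the plan says.** Section 3.c admits adults newly admitted to the center and "prescribed any FDA-approved OUD medication", with no restriction on formulation or visit interval.

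Section 5 defines the compliance rate as completed clinical "contacts per week / number of expected clinical contacts per week". Contacts may be doses, counseling sessions or urine screens. Each organization sets its own benchmark and weights and must produce "a clear equation for how compliance would be calculated". In the worked examples, Center A expects seven methadone doses a week. Center B expects one buprenorphine contact in some weeks and three contacts of different kinds in others.

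The plan handles medication at center level in three places:
- Section 2: the urn randomization balances on number of patients served and percent receiving methadone.
- Section 8.a: before randomization, leaders report the proportion of patients on each OUD medication.
- Section 10.b: the medications a center prescribes are an example of an organization-level covariate, tested as a moderator and otherwise entered as a predictor.

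At patient level, section 9.d.v states: "At the patient-level, we measure biological sex, race/ethnicity, age, and problem severity". Section 9.d.vi adds global health functioning. The patient-level examples in section 10.b are age, race, sex and problem severity. Medication is in none of these lists.

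CM Exposure and CM Sustainment (sections 9.a.i and 9.a.iii) count sessions delivered per patient. Exposure uses the enrolled patients. Sustainment uses a different random sample of 25 patients per center, newly admitted during the Sustainment phase.

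**The concern.** The design treats medication mix as important enough to balance centers on, and the examples show that contact frequency follows medication. Yet the models name no term for the medication of the patients actually analyzed.

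That matters because of timing. Centers are randomized first and patients are enrolled afterwards, at roughly a quarter of new admissions. The Sustainment sample comes from admissions later still. A center's pre-randomization proportions need not describe either group. If medication is related to how many sessions a patient receives, two things follow:
- Patient differences within a center add noise to both session counts.
- If the enrolled mix drifts apart between arms after randomization, the difference is read as an effect of condition.

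Medication may also be related to abstinence and opioid-related problems, so the same gap applies to the secondary outcomes.

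**Working it through.** **The plan's own figures.** Section 4.c: 17 new patients a month × 6 = 102 per center. 25% of 102 = 25.5, taken as 25, and 30 × 25 = 750. These agree. About 77 of 102 new patients per center are therefore not in the analyzed sample, so the center's mix and the sample's mix can differ. The documents give no medication shares, visit intervals, session standard deviation or power calculation.

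**Assumptions, none from the documents.** Two kinds of patient receive on average 8 or 2.5 sessions (gap g = 5.5). Between-center SD is 1.5 and within-center SD is 3. There are 15 centers per arm and 25 patients per center. The share of the low-count kind has mean m and between-center SD s. The staff level is ignored.

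**Formulas.** Between-center variance due to mix: B = g²s². Within-center variance due to mix: W = g²(m − m² − s²). Standard error of the condition effect:
- unadjusted: √[(2/15)(1.5² + B + (9 + W)/25)]
- center share removed: √[(2/15)(1.5² + (9 + W)/25)]
- patient-level term: √[(2/15)(1.5² + 9/25)] = √0.348 = 0.590

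For m = 10% and s = 10 points: B = 30.25 × 0.01 = 0.3025 and W = 30.25 × 0.08 = 2.42. Unadjusted: √[(2/15)(2.25 + 0.3025 + 0.4568)] = 0.633. Center: √[(2/15)(2.25 + 0.4568)] = 0.601.

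| Share (SD) | Formula: unadjusted / center / patient | Simulated: unadjusted / center / patient |
|---|---|---|
| 5% (5) | 0.604 / 0.596 / 0.590 | 0.60 / 0.61 / 0.59 |
| 10% (10) | 0.633 / 0.601 / 0.590 | 0.63 / 0.61 / 0.59 |
| 20% (15) | 0.679 / 0.608 / 0.590 | 0.67 / 0.63 / 0.60 |

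Simulated, the patient-level model beats the center-level one by 1 − 0.59/0.61 = 3% in the first two rows and 1 − 0.60/0.63 = 5% in the third. The formula gives 1%, 2% and 3%. It is smaller because it leaves out the cost of estimating a center-level slope from 30 centers. If the patient term is added to a center term that stays in the model, that cost remains, so the smaller figures are the better guide.

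**Bias.** If the share differs by 10 points between arms among the patients enrolled, the contrast shifts by 0.10 × 5.5 = 0.55 session. Simulation gave about 0.57. Adjusting for the center's baseline share did not remove it, because the imbalance arose afterwards. A patient-level term did.

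**Sensitivity.** With a gap of 2 sessions at m = 10% and s = 10 points, W = 4 × 0.08 = 0.32. The center-adjusted standard error is √[(2/15)(2.25 + 9.32/25)] = 0.591, so the precision gain is about 0.2%. The bias falls to 0.10 × 2 = 0.20 session.

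**Weeks with no expected contact.** The maximum of 78 draws in section 5 reproduces (1 + 2 + … + 12) and needs a defined rate in all 12 weeks. With contacts only in weeks 1, 5 and 9, total draws would be 3 if empty weeks reset the count, 6 if they are skipped, and 15 if they advance the count without a draw. These are draws, not the endpoint.

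**The case against.** The plan already controls medication mix where a cluster trial is most exposed. It balances on percent methadone, collects medication proportions before randomization and allows an organization-level medication covariate. This stands: center-level adjustment recovers most of the precision lost to mix (0.679 to 0.608 of a possible 0.590 at a 20% share). The covariate lists are also introduced as examples, so the accurate statement is that no patient-level medication term is named, not that none could be fitted.

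The route to arm imbalance is only weakly evidenced. Front-desk staff offer contact forms to all new patients, and research staff screen and consent them. The provider bonus for patients reaching 10 sessions could influence enrollment in E-ATTC, but it does not run in the Sustainment phase, where the sample is drawn at random. The bias is conditional on an imbalance that the documents do not show.

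The calculation adjusts for the kind of patient that drives the session count. Recorded medication is only a proxy for that, since centers set expected contacts themselves. The gains shown are upper limits for the proposed term.

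A reader might go further and infer that a patient's visit schedule caps the session count, or that the undefined rate in a week with no expected contact corrupts the primary outcomes. The documents do not support either. The formula decides draws, while the endpoints count sessions. Section 5 describes a session that goes ahead, with praise, when the benchmark is missed. Nothing ties sessions to medication visits. Contacts include counseling and urine screens, no enrolled patient is described as seen less than weekly, and CM Exposure is counted over 9 months with a stated maximum of 24.

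**Conclusion.** The point holds as a modest gap in covariate specification. Medication is used to balance centers and is named as an organization-level covariate, but it is absent from the patient-level covariates measured or modeled. Center-level control cannot describe patients enrolled after randomization or the Sustainment sample.

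Under the assumed values, the standard error is about 3% to 5% lower than with center-level adjustment, or 1% to 3% if the center term is kept. The stronger reason to act is protection against a post-randomization difference in mix: about 0.55 session per 10 points at a gap of 5.5, and 0.20 at a gap of 2. Both figures depend on a mix and a gap that the documents do not give. No size can be put on the effect for the patient outcomes.

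The week with no expected contact is a matter of clarification only. Section 5 sets as a goal a "prize draw to patients at least once per week" and also says "Failure to attain the benchmark or failure to attend the prize draw session resets draws for the next week down to one". It does not say how these apply when nothing was due, and leaves the equation to each center.

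**What to change.** Record each patient's prescribed medication and formulation at admission. The screener already has to confirm a prescription for enrolled patients, and the chart extraction can supply the field for the Sustainment sample. In section 10.b, name it as a pre-specified patient-level covariate, alongside the center's percent methadone, in the models for CM Exposure, CM Sustainment, Opioid Abstinence and Opioid-Related Problems. Use medication at admission rather than the center's expected contacts, which are defined during Preparation, after randomization. Show the estimate without the term as well, so that readers can see how far it moves.

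The cost is one data field and one model term (more than one coefficient if several medication categories are kept). It is estimated from patients, so it uses no center-level degrees of freedom.

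Separately, the weekly formula, the weekly goal and the reset rule in section 5 should be reconciled for weeks in which no contact is expected. This review does not propose which rule should apply.

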1. **Study Purpose.** The primary purpose of this study is to experimentally evaluate two different comprehensive training models to train opioid treatment centers in an evidence-based behavioral treatment called contingency management (CM), which is the provision of motivational incentives for reaching specific treatment benchmarks. An exploratory goal of this study is to test whether theorized mechanisms of change – implementation climate and leadership engagement – mediate the effect of implementation condition on outcomes. Conduct of this study will address critical public health needs by (a) informing how CM, an evidence-based practice, should be implemented in OUD treatment centers, (b) improving the outcomes of OUD patients receiving treatment in the community, and (c) advancing knowledge about why and how implementation strategies work.
2. **Overview of Study Design.** A Type 3 Hybrid Trial will be conducted collecting data on both implementation and patient outcomes. We will use a 3-cohort staggered cluster RCT design. The unit of randomization will be opioid treatment centers. Centers will receive one of two comprehensive training conditions: the standard training provided by the New England Addiction Technology Transfer Center (ATTC training) or an enhanced condition that also provides leadership coaching and provider incentives (E-ATTC training). The primary research activities will be measuring the effectiveness of the training initiatives by gathering data from organizations, providers and patients.

Every 12-16 months, 10 OUD centers will be randomly selected to initiate study activities (10 centers X 3 cohorts = 30 centers). Prior to randomization, each center will complete a Baseline Organizational Assessment (described further in the Measures section) to collect organizational background data (e.g., years in operation, number of patients served annually, number of staff, medications prescribed, implementation readiness). Using these data, urn randomization procedures (balancing on number of patients served and percent of patients receiving methadone) will be used to randomize centers to either the ATTC or the E-ATTC condition. Centers in both conditions will complete a 5-month Preparation phase, a 9-month Implementation phase, and a 12-month Sustainment phase (26 months total). In both conditions, providers will record their delivery of CM in the electronic medical record and will audio record one CM session per month.

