Incentive amounts are designed to enable staff to, on average, earn bonuses that during a 12-month period would comprise about 6% of their mean annual base salary of US \$45,000. Prior P4P research^{18,19} has suggested that bonuses between 4 and 7% are large enough to significantly improve staff performance, yet modest enough to be practical for community treatment centers to implement. Provision of incentives will follow the exact same schedule of provision of performance feedback reports described in 7a. Sessions must be submitted by the last day of the month and must be from that calendar month. Within 2-4 weeks following submission of recordings, providers in the E-ATTC condition will receive email notifications from research staff containing their performance feedback reports, as well as confirmation of their achievement of CM Exposure and CM Competence for the prior month. CM staff enrolled in the E-ATTC condition will receive payments via cash, check, or Clincard.

8. Data Collection Procedures.

- a. *Organizational background form.* Prior to randomization, leaders at each center will collaboratively complete an Organizational Background Form via Qualtrics. Data collected will include, but not be limited to: number of patients, proportion of patients on different OUD medications, number of staff, average staff tenure, and years in operation.
- b. *Staff surveys.* After randomization, CM staff and leadership staff will complete two online Qualtrics surveys: one at the start of the Preparation phase and one at the midpoint of the Implementation phase. The first survey (30-45 minutes) will contain the following measures: Provider Demographics, Organizational Readiness for Change, Attitudes towards CM, and putative mediators (i.e., Implementation Climate, Leadership Engagement). The second survey (15-30 minutes) will only evaluate the putative mediators. Participating staff will receive \$25 for the first and \$20 for the second survey. We attained 82% or higher completion rates on comparable staff follow-up surveys in the New England ATTC pilot.

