- b. For the **Primary and Secondary Aims**, we test a series of multilevel models in which patients (Level 1) are embed within staff (Level 2) and within centers (Level 3). Consistent with Raudenbush and Bryk's multilevel modeling approach,³² the proportion of variance to-be-explained at each level will be examined as an initial step. Next, following a decomposed-first strategy that advocates for starting with moderation-focused hypotheses to avoid biases associated with conflated effects,³³ we conduct multilevel regressions testing the extent to which our covariates significantly moderate the hypothesized relationship between condition and outcome. We test covariates at three levels: organizational (e.g., years of operation, number of patients, medications prescribed, implementation readiness), staff (e.g., tenure, education, CM attitudes), and patient (e.g., age, race, biological sex, problem severity). If moderation is not found, covariates will be controlled for as predictors. Condition assignment (ATTC vs. E-ATTC) will be the primary independent measure of interest for analyses. In addition to reporting statistical significance, we will report the effect size (ES) using Cohen's d .³⁴
- c. For the **Exploratory Aim**, we again test a series of 3-level models. For each mediator, the average correlation within group (r_{wg}) will be computed to determine whether aggregation of staff level responses to the organizational-level is warranted. Values of r_{wg} range from -1.00 to 1.00, with values $\geq .60$ representing acceptable agreement.³⁵ Centers with r_{wg} values $< .60$ will be excluded from analysis. Exploratory analyses will apply a Baron and Kenny³⁶ style mediation approach,

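### CM attitudes is used as a baseline covariate in the Primary and Secondary models but is measured only after randomization, and the timing of implementation readiness is contradictory

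*Combined protocol and SAP*

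**What the plan says.** **Timing.** Section 8.b (Staff surveys): "After randomization, CM staff and leadership staff will complete two online Qualtrics surveys: one at the start of the Preparation phase". On content: "The first survey (30-45 minutes) will contain the following measures: Provider Demographics, Organizational Readiness for Change, Attitudes towards CM, and putative mediators", the mediators being implementation climate and leadership engagement. The second survey, in mid-Implementation, repeats the mediators only.

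**Label.** Section 9.d (Covariates) lists both implementation readiness and CM attitudes under this description: "We measure potential baseline covariates at the patient, staff, and organization level. These measures are only administered at baseline".

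**Use.** For the Primary and Secondary Aims, section 10.b names the covariates at organization level as "organizational (e.g., years of operation, number of patients, medications prescribed, implementation readiness") and at staff level as "staff (e.g., tenure, education, CM attitudes"). Each is first tested as a moderator of the condition effect. Then: "If moderation is not found, covariates will be controlled for as predictors".

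**A different timing for readiness.** The Overview of Study Design (item 2 of the Detailed Study Methodology) says: "Prior to randomization, each center will complete a Baseline Organizational Assessment". It names implementation readiness among the data collected there. Section 8.a describes the pre-randomization form with an open-ended list that mentions neither readiness nor CM attitudes.

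**Mediators.** Section 9.c places both mediator scales in the same two surveys. The climate scale asks how far CM "is expected, supported, and rewarded within their center".

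**The concern.** A covariate can safely sharpen or adjust a randomized comparison when assignment cannot have influenced it. A score collected after allocation has no such guarantee. If E-ATTC staff answer the attitude items knowing their condition, part of the condition effect may already sit in the score. Holding the score constant then takes that part out of the estimate.

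The Primary Aim asks for the total effect of E-ATTC against ATTC, so this would change what the models estimate. The moderation step has a related difficulty: an interaction with a score that condition may have moved does not cleanly describe which kinds of staff respond more. With no earlier attitude score, the trial could not tell a shift caused by assignment from chance imbalance among 30 centers.

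**Working it through.** The plan gives no figure to reproduce here: no power calculation, no effect size, and no expected shift in any survey scale. The check has two parts, tracing each variable to its measurement and then sizing the possible bias under stated assumptions.

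**1. Where each variable is measured**

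| Variable | Before randomization | After randomization | Role |
|---|---|---|---|
| CM attitudes | nowhere stated | first staff survey (8.b), once | moderator or adjuster (10.b) |
| Readiness | yes, by the Overview of Study Design | yes, by 8.b, as Organizational Readiness for Change | moderator or adjuster (10.b) |
| Climate, leadership engagement | nowhere stated | both surveys (8.b, 9.c) | mediators, Exploratory Aim only |
| Years of operation, patient numbers, medications | organizational form | – | moderator or adjuster (10.b) |
| Staff tenure, education | nowhere stated | Provider Demographics in the first survey | moderator or adjuster (10.b); assignment cannot change the answer |

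CM attitudes is the secure case: it has one measurement, after randomization, and enters the models in either branch of 10.b. Readiness is a contradiction between two sections.

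**2. Size**

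In a linear model:

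adjusted condition effect = total effect − b × s

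Here s is the difference in the covariate caused by condition (SD units), and b is the slope of the outcome on the covariate within condition. The slope need not be causal for the formula to hold.

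The only slope of this kind in the documents is .18 (section 9.c.ii), for leadership engagement predicting staff-level fidelity. That scale is not an adjuster, so .18 is only an illustration. The other slopes and all shifts are assumptions. Values of b × s, in SD:

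| b | s = 0 | s = 0.1 | s = 0.2 | s = 0.3 | s = 0.5 |
|---|---|---|---|---|---|
| .18 | 0 | 0.018 | 0.036 | 0.054 | 0.090 |
| .30 | 0 | 0.030 | 0.060 | 0.090 | 0.150 |
| .50 | 0 | 0.050 | 0.100 | 0.150 | 0.250 |

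**3. Check by simulation**

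The setting was 30 centers with 4 staff each, 1,500 runs per row, and an assumed total effect of 0.50.

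| b, s | 0.50 − b × s | Adjusted for post-randomization score | Adjusted for pre-randomization score |
|---|---|---|---|
| .18, 0.2 | 0.464 | 0.461 | 0.498 |
| .30, 0.3 | 0.410 | 0.409 | 0.498 |
| .50, 0.5 | 0.250 | 0.256 | 0.507 |
| .30, 0 | 0.500 | 0.503 | 0.503 |

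The simulation used ordinary least squares on staff-level data, not the plan's three-level model. It confirms the algebra but does not estimate the bias in this trial.

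**The case against.** The strongest reply is that contamination is possible but not shown. The survey comes as Preparation begins. Section 7.b puts the pay-for-performance overview at a planning meeting with center leadership, after the feedback summary, and the leaders' center-specific coaching calls in the last two months of Preparation. The documents show no condition-specific contact with CM staff before the survey, and they do not say when a center learns its allocation. The attitude measure concerns CM's effectiveness and acceptability, and nothing shows that news of provider bonuses changes those views. All of this stands, and it makes the harm conditional. It does not remove the problem: 8.b puts the survey explicitly after randomization, and the blinding in section 9.a covers record extraction and session rating, not survey respondents.

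A reader might infer three stronger things that the documents do not support:

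- **That staff already know of the $200 and $50 bonuses when surveyed.** No section says so.
- **That readiness is settled as a post-randomization adjuster.** The Overview places it before randomization, and 10.b groups it with organizational-form variables. The different label in 8.b may even mean two measurements. What stands is that the sections conflict.
- **That climate and leadership engagement are also adjusters.** Section 10.b does not list them. For the Exploratory Aim, 10.c describes no change score or subtraction of a starting value. The point there is only that no pre-randomization measurement exists.

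**Conclusion.** The point holds for CM attitudes: a score taken after randomization is treated as baseline and enters the Primary and Secondary models as a moderator or adjuster. Whether this biases the result depends on a shift that the documents neither report nor rule out.

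Using the documents' one related slope and assumed shifts of 0.1 to 0.5 SD, the understatement would be modest. The figure of 0.25 SD needs a slope and a shift of 0.5 together, both assumed, and should not be read as an estimate. The direction is also conditional: it is toward the null only if E-ATTC assignment raises attitudes and higher attitudes go with better outcomes.

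For readiness, the conclusion is that the sections must be reconciled. For the mediators, it is limited to the missing pre-randomization value. The matter should be corrected because the protection is cheap; the documents do not show that the primary results would be wrong.

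**What to change.** 1. **Section 8.b:** have the first staff survey completed before randomization, alongside the Organizational Background Form, or at least before the center is told its condition. This also gives the mediators a measurement that precedes assignment. The mid-Implementation survey stays where it is.
2. **Readiness:** reconcile the Overview of Study Design with 8.b, and state that the pre-randomization measurement feeds the models in 10.b.
3. **If the survey cannot be moved, and for replacement staff surveyed later:** leave CM attitudes and any post-randomization readiness score out of the primary adjustment and moderation models. Keep covariates that assignment cannot change: the organizational-form variables, staff tenure and education, and patient characteristics such as age, race and sex. Report models that add the survey scores as sensitivity analyses.

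**Cost:** one existing online survey is reordered. Staff may have to be identified slightly earlier, unless they are already named in the Organization Participation Agreement Form, which section 4.b suggests. A center that withdraws before randomization would leave some unused survey responses.
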